13. CD4 and CD8 Counts and HLA typing are performed by central laboratory. Collection is described in the Laboratory Manual. If HLA sample is rejected for analysis, an additional sample may be collected at a later time point
14. Thyroid panel should be collected during ODD NUMBERED cycles only (i.e. every 6 weeks). Blood draws may be taken up to 72 hours before each required dosing cycle. Unresolved abnormal labs considered drug related AEs should be followed until resolution. Panel not required at EOT if labs are within normal range during treatment.
15. Hematology, serum chemistry: Blood draws may be taken up to 72 hours before each dosing cycle where study drug is administered.

16. Coagulation Panel may be repeated at same frequency as hematology/serum chemistry if clinically indicated; beginning at Cycle 6 frequency may be reduced to every 12 weeks unless clinically indicated.
17. Pregnancy Test: Serum pregnancy test required at screening, and urine pregnancy tests are required before doses on Day 1 of each cycle and EOT for WOCBP.
18. Whole blood for PBMC and Serum and plasma for immune monitoring collected and processed per Laboratory Manual. Samples should be collected prior to study drug administration. Cycle 2 Day 15 collection should be taken on day of biopsy. Additional samples may be collected at Investigator's discretion.
19. Blood for CRS-207 Surveillance will be collected at EOT or 7 days after last CRS-207 dose to assess clearance of CRS-207. Obtain sample(s) prior to initiation of antibiotics (blood must additionally be collected from the central venous access device if applicable). After last dose of CRS-207, blood will continue to be collected at [REDACTED]. Collection and shipment are described in the Laboratory Manual.
20. Pembrolizumab will be administered via IV infusion for 30 minutes. Obtain vital signs (BP, pulse, respiratory rate, temperature) prior to, and immediately following each pembrolizumab infusion. Pembrolizumab may be administered up to 3 days before or after the scheduled Day 1 of each cycle due to administrative reasons. If subjects on same-day dosing schedule experience severe infusion-related reactions related to the pembrolizumab infusion, the CRS-207 infusion may be delayed to Day 2.

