6.2.3 Dosing Eligibility and Delayed Dosing

Subjects must have adequate organ function confirmed (as defined by the laboratory values in Table 6-1) prior to each dosing cycle where CRS-207 is administered; laboratory tests may be performed up to 3 days before dosing.

Table 6-1 Dosing-Eligibility Requirements

Hematologic	Renal	Hepatic
WBC \geq 3000/ μ L	Creatinine \leq 1.5 \times ULN	AST/ALT \leq 5 \times ULN
ANC \geq 1000/ μ L		Bilirubin \leq 1.5 \times ULN OR \leq 3 \times ULN if due to Gilbert's disease
Platelets \geq 90,000/ μ L		
Hemoglobin \geq 8 g/dL		

ALT = alanine aminotransferase; ANC = absolute neutrophil count; AST = aspartate aminotransferase; ULN = institutional upper limit of normal; WBC = white blood cell

Subjects who do not meet dosing eligibility requirements will be monitored; dosing may be delayed up to 2 weeks, after which time it will be considered missed and the subject would continue onto the next scheduled dose. If a dose is delayed more than 2 weeks, contact the Medical Monitor for further instruction on continued dosing.

Pembrolizumab may be administered up to 3 days before or after the scheduled Day 1 of each cycle due to administrative reasons. If subjects on same-day dosing schedule experience severe infusion-related reactions related to the pembrolizumab infusion, the CRS-207 infusion may be delayed to Day 2. CRS-207 must be administered one day after pembrolizumab administration. If the subject experiences a new AE or is recovering from an AE, CRS-207 administration may be delayed up to 7 days and the Sponsor must be notified. If a dose of CRS-207 is delayed beyond 7 days of pembrolizumab, the dose of CRS-207 should be withheld until the next cycle.

Dosing interruptions are permitted in the case of medical / surgical events or logistical reasons not related to study therapy (e.g. elective surgery, unrelated medical events, vacation, and/or holidays). Subjects should be placed back on study therapy within 3 weeks of the scheduled interruption, unless otherwise discussed with the Sponsor. The reason for interruption should be documented in the Subject's study record.

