Grade 2 Requires therapy or infusion interruption but responds promptly to symptomatic treatment (e.g., antihistamines, NSAIDs, narcotics, IV fluids); prophylactic medications indicated for ≤ 24 hrs	
Stop Infusion.
 
Additional appropriate medical therapy may include but is not limited to:
 
IV fluids Antihistamines NSAIDs Acetaminophen Narcotics
 
Increase monitoring of vital signs as medically indicated until the subject is deemed medically stable in the opinion of the investigator.
 
If symptoms resolve within 1 hour of stopping drug infusion, the infusion may be restarted at 50% of the original infusion rate (e.g. from 100 mL/hr to 50 mL/hr). Otherwise dosing will be held until symptoms resolve and the subject should be premedicated for the next scheduled dose.
 
Subjects who develop Grade 2 toxicity despite adequate premedication should be permanently discontinued from further study drug treatment
	
Subject may be premedicated 1.5h (\pm 30 minutes) prior to infusion of pembrolizumab with:
 
Diphenhydramine 50 mg po (or equivalent dose of antihistamine).
 
Acetaminophen 500-1000 mg po (or equivalent dose of analgesic).

NCI CTCAE Grade	Treatment	Premedication at Subsequent Dosing
Grades 3 or 4 Grade 3: Prolonged (i.e., not rapidly responsive to symptomatic medication and/or brief interruption of infusion); recurrence of symptoms following initial improvement; hospitalization indicated for other clinical sequelae (e.g., renal impairment, pulmonary infiltrates) Grade 4: Life-threatening; pressor or ventilatory support indicated	Stop Infusion. Additional appropriate medical therapy may include but is not limited to: Epinephrine** IV fluids Antihistamines NSAIDs Acetaminophen Narcotics Oxygen Pressors Corticosteroids Increase monitoring of vital signs as medically indicated until the subject is deemed medically stable in the opinion of the investigator. Hospitalization may be indicated. **In cases of anaphylaxis, epinephrine should be used immediately. Subject is permanently discontinued from further study drug treatment.	No subsequent dosing

Appropriate resuscitation equipment should be available at the bedside and a physician readily available during the period of drug administration.

[figure not shown]
For further information, please refer to the Common Terminology Criteria for Adverse Events v4.0 (CTCAE) at <http://ctep.cancer.gov>

Other Allowed Dose Interruptions for Pembrolizumab

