7.1.2 Assessment of Adverse Events by the Investigator

The Investigator will assess the severity (intensity) of each AE and the potential relationship between the AE and the study medication.

Assessment of Severity:

The severity of all AEs should be graded according to the NCI-CTCAE v. 4.03 (<http://ctep.cancer.gov/reporting/ctc.html>). For AEs not listed in the CTCAE, the following grading system should be used:

- Mild (CTCAE Grade 1): Transient symptoms, awareness of sign/symptom, but easily tolerated and no interference with subject's daily activities
- Moderate (CTCAE Grade 2): Marked signs/symptoms that interfere with subject's usual activities, but still acceptable
- Severe (CTCAE Grade 3): Incapacitating signs/symptoms which cause considerable interference with the subject's daily activities, unacceptable
- Life-threatening (CTCAE Grade 4): Life-threatening or disabling AE
- Death (CTCAE Grade 5): Death-related AE

Attribution:

The Investigator is obligated to estimate the relationship between the investigational agents and the occurrence of each AE or SAE using best clinical judgment. Other causes, such as the underlying disease, concomitant therapy, other risk factors, and the temporal relationship of the

event to the investigational agents should be considered and investigated. The Investigator should consult the IB or product labeling information for marketed products in the determination of the assessment. The Investigator should consider all possible etiologies for the AE and render a causality assessment based on the most likely contributing factor to the AE.

There may be situations when an SAE has occurred and the Investigator has minimal information to include in the initial report. However, the Investigator must assess causality for every event before the transmission of the SAE. The Investigator may change his or her opinion of the causality in light of follow-up information, amending the SAE report.

The assessment of the relationship between the AE and the study medication will be determined using one of the following attribution categories as outlined in the NCI Guidelines: Adverse Event Reporting Requirements (2013).

RELATIONSHIP	ATTRIBUTION	DESCRIPTION
Unrelated to investigational agent/intervention	Unrelated	The AE is clearly NOT related to the intervention
	Unlikely Related	The AE is doubtfully related to the intervention

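### Table 6-5 stops an unnamed study drug after a serious pembrolizumab infusion reaction, while Protocol 6.2.3 and footnote 20 let CRS-207 be given on Day 2

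*Protocol*

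**What the plan says.** Protocol Table 6-5 (in 6.3.5.2) sets the response to pembrolizumab infusion reactions by grade. The Grade 3-4 row ends with "Subject is permanently discontinued from further study drug treatment", and its premedication column rules out any later dose. The Grade 2 row adds "Subjects who develop Grade 2 toxicity despite adequate premedication should be permanently discontinued from further study drug treatment". Neither row names the agent.

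Protocol 6.2.3 deals with the same event from the CRS-207 side: "If subjects on same-day dosing schedule experience severe infusion-related reactions related to the pembrolizumab infusion, the CRS-207 infusion may be delayed to Day 2". Footnote 20 to Tables 1-1 and 1-2 repeats this for "severe infusion-related reactions related to the pembrolizumab infusion, the CRS-207 infusion may be delayed to Day 2". Neither sentence sets a condition.

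Section 6.2.3 also covers a new or resolving adverse event: "CRS-207 administration may be delayed up to 7 days and the Sponsor must be notified". If the delay goes beyond 7 days after pembrolizumab, "the dose of CRS-207 should be withheld until the next cycle".

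Protocol 6.2.4 and 6.3.1.1 let a subject continue on one agent after an unacceptable toxicity, given the Sponsor Consultation Form and Medical Monitor approval.

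**The concern.** Two sites could face the same Grade 3 reaction, act in opposite ways, and both cite the protocol. One would stop both drugs for good under Table 6-5. The other would infuse CRS-207, a live attenuated bacterium, the next day under 6.2.3. Protocol 4.1.4 lists fever, chills, vomiting and hypotension among the common effects of CRS-207. Giving it before the first reaction has settled could compound the event and blur attribution.

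What is at stake is subject safety and consistent dosing between sites. No estimate, interval or analysis set depends on it.

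**Working it through.** No arithmetic applies. The check sets the rules side by side.

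**1. Which agent is meant?**
- *Both agents:* the Study Drug column of Table 6-2 lists pembrolizumab and CRS-207, so the literal term covers both.
- *Pembrolizumab only:* Table 6-5 is titled for pembrolizumab infusion reactions, and its Grade 2 premedication is given "prior to infusion of pembrolizumab with". This reading is more likely, but the protocol never states it. Table 6-4, in the same section, does name pembrolizumab in its action column.

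**2. Does *severe* in 6.2.3 reach the Grade 3-4 row?**
- Exclusion criterion 28 (6.2.2) equates severe hypersensitivity to either agent with Grade 3 or higher.
- The text introducing Table 6-5 pairs severe with life-threatening reactions, and the table makes Grade 4 the life-threatening grade. That leaves Grade 3 as severe.
- Secondary support is the scale in 7.1.2, "Severe (CTCAE Grade 3): Incapacitating signs/symptoms which cause considerable interference", which applies only to events not listed in the CTCAE.

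So the two rules address the same reactions.

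**3. Reading A, both agents.** Table 6-5 forbids any further CRS-207 after a Grade 3-4 reaction, while 6.2.3 and footnote 20 permit it on Day 2. That is a direct conflict. The repeat Grade 2 row does not conflict, because a Grade 2 reaction is not severe.

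**4. Reading B, pembrolizumab only.** Take a Grade 3 reaction of 3 days or less, treated without steroids:

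| Rule | Does it require approval before CRS-207? |
|---|---|
| 6.3.1.1, Grade 3 non-hematologic, non-laboratory toxicity | No. It counts as unacceptable only if it lasts more than 3 days. |
| 6.3.1.1, systemic steroids for an immune-mediated reaction | No. None were given. |
| 6.2.4 and 6.3.1.1, single-agent approval | No. It follows an unacceptable toxicity, and there is none. |
| 6.3.5.2, Medical Monitor consultation on CRS-207 | No. It is written for the immune-related events of Table 6-4 and not repeated for infusion reactions. |
| 6.3.4.3, contact with the Medical Monitor | No. It covers events attributable to CRS-207. |
| 6.3.8, steroid restriction | No. No steroids were given. |
| 6.2.3, delay for an adverse event | No. It asks for notification, not approval. |

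Pembrolizumab has ended permanently, and CRS-207 may follow with Sponsor notification at most. The case is plausible: 6.3.5.2 says these reactions usually clear within 24 hours, and Table 6-5 lists corticosteroids as one optional treatment among several.

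A Grade 2 reaction despite premedication leaves the same gap on this reading. Pembrolizumab stops and no approval step is triggered.

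**5. Cases already covered.** A Grade 4 non-laboratory reaction is itself an unacceptable toxicity. After systemic steroids within the 14-day window, 6.3.8 already requires Medical Monitor approval. Section 6.3.5.2 also says that withholding pembrolizumab during the Safety Run-in defines an unacceptable toxicity. That sentence sits under the immune-related heading. If it extends to infusion reactions, it closes the gap for run-in subjects, and only at Cycle 2, because Cycle 1 uses consecutive-day dosing for everyone.

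**The case against.** The strongest reply is that the ungated dose exists on only one reading. If *study drug* means both agents, Table 6-5 prohibits the CRS-207 dose. What remains is a clash of wording. This stands: the gap is conditional on Reading B. It does not remove the point, because Reading A yields a contradiction instead.

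A second reply is that the Day 2 sentence is a timing rule and does not authorise single-agent therapy, for which the only express route needs Medical Monitor approval. That is a reasonable view of intent. However, the express route is tied to an unacceptable toxicity, which this case is not, and nothing in 6.2.3 refers the site to it.

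A reader might go further and infer that the protocol lets a site give CRS-207 alone the next day on its own judgement. The documents do not support that:
- Some or all of the Day 1 pembrolizumab dose may already have been given, and pembrolizumab on Day 1 followed by CRS-207 on Day 2 is the standard Cycle 1 sequence.
- Section 6.2.3 requires Sponsor notification when CRS-207 is delayed for an adverse event.
- The laboratory criteria in Table 6-1 still apply, and the site may delay or withhold the dose.

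Comparison with Grade 2 pneumonitis, where the Medical Monitor is consulted, adds little. That event calls for corticosteroids, which the case here excludes. No passage shows added CRS-207 risk after a short, steroid-free reaction.

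**Conclusion.** The dosing rules are wrong as written. On one reading Table 6-5 contradicts 6.2.3 and footnote 20. On the other, a short Grade 3 reaction without steroids, or a Grade 2 reaction despite premedication, can be followed by CRS-207 without an approval step. The contradiction assumes that *severe* means Grade 3 or higher, which exclusion criterion 28 and the text of 6.3.5.2 support.

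Severity is minor. The Day 2 option applies to same-day dosing, so from Cycle 2 onward. The number of subjects affected is assumed to be small, but the documents give no reaction rate and no count can be offered. The SAP and every statistical result are untouched. Nothing in the documents shows that any subject was dosed in conflict with either rule.

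**What to change.** 1. In Table 6-5, replace *study drug* with *pembrolizumab* in both places: the Grade 3-4 row and the repeat Grade 2 sentence.
2. In 6.2.3 and footnote 20, keep the Day 2 option and add a condition. After any infusion reaction that permanently stops pembrolizumab (Grade 3-4, or Grade 2 despite premedication), CRS-207 may be given only once the reaction has resolved, with the Sponsor Consultation Form and Medical Monitor approval, and subject to the steroid restriction in 6.3.8.

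The condition must cover the Grade 2 case. Naming pembrolizumab there without an approval step would make explicit the same ungated CRS-207 dosing that the change closes for Grade 3-4.

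The cost is protocol wording in four places and one extra approval in what should be a few subjects. No SAP change is needed. SAP 3.5 records that every subject had completed the end-of-treatment visit by 31 January 2018, so the change serves the protocol text and any reuse of it, not doses already given.

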6.3.6 Antibiotics

To eliminate any potentially residual CRS-207, subjects will be administered antibiotics at the EOT visit or 7 days after the last dose of CRS-207 (for patients continuing on pembrolizumab), prior to receiving subsequent cancer-related (non-study) therapy.

[REDACTED]

[REDACTED]

[REDACTED]

Consult the package inserts for amoxicillin, trimethoprim, and sulfamethoxazole for product information on dosage and administration, contraindications, warnings/precautions, adverse reactions, and drug interactions.

6.3.6.1 Suspected Infection with CRS-207

Suspected infection with CRS-207 and/or Listeria is considered an adverse event of special interest (AESI; [Section 7.3.5](#)) and should be reported following SAE reporting procedures ([Section 7.3](#)) irrespective of temporal relationship to study drug administration. This includes scheduled blood cultures during surveillance monitoring that are positive for CRS-207 or if a subject presents with symptoms suspicious for a Listeria-like infection and/or is tested positive for Listeria at a local hospital/clinic.

In the case of suspected persistent CRS-207 or Listeria infection, blood, urine and stool samples should be obtained in duplicate. One set of samples should be cultured locally for Listeria per institutional guidelines. Culture of cerebrospinal fluid should be obtained for subjects with suspected central nervous system infection. In such instances, analysis of cerebrospinal fluid should also include cell count, protein, glucose, and Gram stain. If samples are positive for Listeria, the Sponsor must be notified immediately, and the duplicate samples and Listeria isolate must be sent for testing to confirm CRS-207. Instructions on collection, storage and shipping of samples for CRS-207 testing are provided in the Laboratory Manual

If infection with CRS-207 is confirmed or suspected, IV antibiotics (see below) should be initiated as soon as possible and follow-up cultures obtained periodically to confirm absence/clearance of any CRS-207 infection. The Medical Monitor should be consulted regarding continuation of study drug treatment and treatment of suspected or confirmed infection.

Antibiotic Treatment for CRS-207 Infection

6.3.7 Concomitant Medications and Procedures

Subjects may receive concomitant medications as required, unless specifically restricted or prohibited in this study (Section 6.3.8). Minor procedures such as dental work, skin biopsy, celiac plexus block, biliary stents, mediport/port insertion, and video-assisted thoracic surgery biopsy are allowed; however, CRS-207 should not be administered within 14 days of the procedure or until the investigator determines there is no additional risk to the subject.

During the course of the study, subjects are anticipated to continue the use of prescribed medications identified during the screening procedures, consistent with study inclusion and exclusion criteria.

Concomitant medications used in this study include:

- Acetaminophen (paracetamol) prior to each CRS-207 infusion
- Antiemetics according to American Society for Clinical Oncology guidelines ([Basch, 2011](#))
- Antipyretics to treat fever or to prevent recurrence of fever post-CRS-207 infusion
- IV narcotics such as morphine or meperidine (per institutional policy) for rigors associated with CRS-207 dosing
- 7-day antibiotic regimen following last dose of CRS-207

6.3.8 Prohibited Medications and Procedures

A subject may be removed from the study for use of prohibited medications or procedures. Approval must be obtained from the Medical Monitor for a subject to continue dosing if a prohibited medication is administered within the specified timeframes. The following therapies are not permitted or restricted during the study:

- Non-study chemotherapy or immunotherapy (approved or investigational)
- TNF pathway inhibitors or PI3 kinase inhibitors
- Palliative radiation
- Live vaccines (examples of live vaccines include, but are not limited to: measles, mumps, rubella, chicken pox, yellow fever, rabies, BCG, and typhoid [oral] vaccine). Seasonal influenza vaccines for injection are generally killed virus vaccines and are allowed. However, intranasal influenza vaccines (e.g. Flu-Mist[®]) are live attenuated vaccines, and are not allowed.
- Any major surgery or surgical procedure; if required must be discussed with the Medical Monitor to determine if it is appropriate for the subject to continue study treatment
- Any other investigational product

If a subject requires an emergent implant of a prohibited device while on therapy, the subject will receive a 14-day IV antibiotic regimen ([Section 6.3.6.1](#)).

In addition, the following medications are only restricted prior to and after CRS-207 infusions as indicated:

- Systemically active steroids for more than 3 days or use of any systemic steroids within 14 days before or after CRS-207 infusion, with the exception of inhaled and topical steroids
- Filgrastim (granulocyte colony stimulating factor; G-CSF) or sargramostim (granulocyte-macrophage colony stimulating factor; GM-CSF) within 14 days prior to or 14 days after CRS-207 infusion
- Prophylactic vaccines (e.g. pneumococcal vaccine, influenza vaccine) within 14 days prior to or after CRS-207 infusion

The following therapies should not be administered during the study unless medically necessary; approval must be obtained from the Medical Monitor for a subject to continue dosing if therapy is given concurrently with study participation:

- General anesthesia or deep sedation
- Aspirin >325 mg/day
- Acetaminophen > 4 g/day
- Systemic antibiotics

There are no prohibited therapies during the Follow-up Period.

If subjects receive immunosuppressive medications on or after study, prophylactic antibiotics to prevent CRS-207 infection are strongly recommended for the duration of the treatment with the immunosuppressant (recommended oral 80 mg trimethoprim / 400 mg sulfamethoxazole once daily or 160 mg trimethoprim / 800 mg sulfamethoxazole (DS) three days a week).

6.3.9 Treatment Compliance

Study treatments will be administered by IV infusion by a qualified health care professional at an approved study site. The date, time, and volume of each dose of study drug administered to each subject must be recorded in the dispensing log for the study and the eCRF.

Antibiotics will be provided to subjects following the last dose of CRS-207 as indicated in [Table 1-1](#) or [Table 1-2](#). Site personnel will contact the subject by telephone to facilitate compliance with antibiotic treatment; subjects will be required to record self-administration of antibiotics in a diary.

